8.5.2 Sampling Plan

Prescriber (HCP) survey

For each selected country, the sample survey will include HCPs identified from cross-referencing haemophilia treatment centre locations listed on the Haemophilia Central website and IQVIA OneKey lists (see [Section 8.4.1](#)).

A screening question will check whether the physician has prescribed Hemlibra® at least once, and therefore can be considered for the survey.

Ideally, the sample HCPs should be proportionally split between the selected countries based on the number of prescribing HCPs in each. However, due to the expected variance of the number of HCPs in targeted countries (reflecting differences in degree of treatment concentration) such a distribution is not always feasible.

A pragmatic split will therefore be implemented to allocate a sufficient size to the less represented strata of the sample and to adjust to the market uptake of Hemlibra® in the countries included. We will then weight back the results according to the real proportion of HCPs in geographic regions from OneKey lists to reduce potential skewness of the overall sample (see [Section 8.5.3](#)).

Patient/Carer survey

For each selected country, the sample patient/carers survey will be distributed by HCPs who have agreed to participate in the patient/carers survey.

8.5.3 Sample Adjustment

Prescriber (HCP) survey

Since the relative weight of each country and each speciality of HCPs, e.g. paediatric haematologist or haematologist, in the final sample may be different from its real proportion, the extrapolation of the raw survey results to the overall target population would not be relevant without adjustment. The survey results will be weighted to reflect the real proportion in order to allow the extension of the survey results to the overall target population. Both unweighted and weighted results will be presented in the report.

A weight variable will be applied to each statistical unit (i.e., the HCPs) during the results calculation in order to correct any over- or under-sampling that may have occurred for a region. This weight variable will indicate how many unit(s) of the population of interest an observation will count in a statistical procedure. Its value will change per geographic region. The weights will be normalised to obtain their sum equal to the sample size.

Patient/Carer survey

Of note, the sample distribution for patients is uncertain, since it depends on sales of Hemlibra®, the level of contribution of HCPs distributing surveys, the number of patients in the practice of participating HCPs, and the response rate of patients. In any case, the sample will be weighted based on the number of patients who received Hemlibra® in each of the represented geographical regions.

8.6 DATA MANAGEMENT

IQVIA will be responsible for data management of this study, including quality checking of the data.

Collected data will be entered and stored in a central database specific to the survey.

A study database will be created by merging the databases of each country together. The study database will be locked once validated.

8.6.1 Data Quality Assurance

IQVIA will be responsible for the data management of this study, including quality checking of the data. IQVIA will produce a Data Quality Review Plan that describes the quality checking to be performed on the data.

Questions are programmed to ensure that they are asked in the appropriate sequence. Skip patterns are clearly indicated. Respondents cannot go back to a question once the question has been answered and they cannot skip ahead. Response options presented in a list are randomized to minimise positional bias. Programming will be reviewed by Quality Control and simulated users (User Testing) prior to implementation.

Data will be checked in terms of consistency before data analysis:

- Removal of duplicates (if required)
- Data labelling and data formatting
- Range and consistency checks for each variable to identify potential non-admissible values
- Cross-check the consistency of data for related variables (if feasible).

If missing values exist, the number of variables with missing values will be indicated. Missing values will be excluded from the calculation of percentages.

Automatic checks for plausibility and consistency will be programmed into the questionnaire tool, which will prevent contradicting values from being entered. IQVIA will not query HCPs' answers to questions in the questionnaire.

Non-admissible values will be avoided by implementation of the appropriate controls in the questionnaire at the time of its completion by the HCPs. Any non-admissible values identified after database lock (if any) will be excluded from the analysis.

The marketing authorization holder will perform oversight of the data management of this study, including approval of IQVIA data management plans and specifications.

The QC team will comply with the Roche's procedures regarding archiving and record management.

8.6.2 Source Data Documentation

Not applicable

8.7 DATA ANALYSIS

The statistical analyses will be described and further detailed in the Statistical Analysis Plan (SAP). The described analysis below might be revised, and adjustments might occur. The final SAP version will include (empty) table shells to be populated for the final study report.

8.7.1 General Considerations

The statistical analysis will be conducted using the SAS software V9.4 or above on Windows™ (SAS Institute, North Carolina, USA).

All the analyses will be descriptive. The statistical results will be presented separately for HCPs and patients/carers, overall for all 13 countries and by region (see Table 3 as an example for HCPs). *Other criteria for grouping may also be used for results presentation e.g., Euro Health Consumer Index.* As some questions may have multiple choices, the proportion of HCPs/patients having provided each possible answer will be described.

Table 3 Mock Tables to Implement in the Statistical and Study Reports

Region/country	Speciality	Speciality	All (unweighted)	All (weighted)
Region 1	(N=xx)	(N=xx)	(N=xx)	(N=xxx)
answer 1	xx (xx.x%)	xx (xx.x%)	xx (xx.x%)	xx (xx.x%)
answer 2	xx (xx.x%)	xx (xx.x%)	xx (xx.x%)	xx (xx.x%)
answer 3	xx (xx.x%)	xx (xx.x%)	xx (xx.x%)	xx (xx.x%)
Region 2	(N=xx)	(N=xx)	(N=xx)	(N=xx)
answer 1	xx (xx.x%)	xx (xx.x%)	xx (xx.x%)	xx (xx.x%)
answer 2	xx (xx.x%)	xx (xx.x%)	xx (xx.x%)	xx (xx.x%)
answer 3	xx (xx.x%)	xx (xx.x%)	xx (xx.x%)	xx (xx.x%)
Region X	(N=xx)	(N=xx)	(N=xx)	(N=xx)
answer 1	xx (xx.x%)	xx (xx.x%)	xx (xx.x%)	xx (xx.x%)
answer 2	xx (xx.x%)	xx (xx.x%)	xx (xx.x%)	xx (xx.x%)
answer 3	xx (xx.x%)	xx (xx.x%)	xx (xx.x%)	xx (xx.x%)
Overall - unweighted results	(N=xx)	(N=xx)	(N=xx)	(N=xxx)
answer 1	xx (xx.x%)	xx (xx.x%)	xx (xx.x%)	xx (xx.x%)
answer 2	xx (xx.x%)	xx (xx.x%)	xx (xx.x%)	xx (xx.x%)
answer 3	xx (xx.x%)	xx (xx.x%)	xx (xx.x%)	xx (xx.x%)
answer 3	xx (xx.x%)	xx (xx.x%)	xx (xx.x%)	xx (xx.x%)
Overall - weighted results	(N=xx)	(N=xx)	(N=xx)	(N=xxx)
answer 1	xx (xx.x%)	xx (xx.x%)	xx (xx.x%)	xx (xx.x%)
answer 2	xx (xx.x%)	xx (xx.x%)	xx (xx.x%)	xx (xx.x%)
answer 3	xx (xx.x%)	xx (xx.x%)	xx (xx.x%)	xx (xx.x%)

Continuous variables will be presented by their number (of valid cases, of missing values [if applicable]), mean, standard deviation, and median, first quantile (Q1), third quantile (Q3), minimum and maximum.

Categorical variables will be presented as the total number and relative percentage per category. These will be the percentage per category.

In case of multiple-choice questions, the frequency of each option provided by the physicians will be reported in the statistical results.

Confidence intervals of 95% will be evaluated, when relevant.

The proportions of correct and appropriate answers to selected questions asked in the questionnaire will be expressed among HCPs and patients/carers who provided answers

to those questions (If missing data exists, it will not be counted as a denominator in proportions).

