7.2 OBJECTIVES

To evaluate whether prescribers and the patients/carers have understood the requirements of and report adherence with the additional RMMs associated with Hemlibra®. The objectives of the study are as follows:

Prescriber (HCP) survey

- Assess prescriber awareness of the Hemlibra® educational program by estimating the proportion of targeted prescribers who acknowledge having received and read the relevant educational materials.
- Assess prescriber knowledge of:
 - the important identified risks of TMA and TEs that may occur if a cumulative amount of >100U/kg/24 hours for 24 hours or more of aPCC is used concomitantly with Hemlibra® and
 - the important potential risk of life-threatening bleeding due to misinterpretation of the standard coagulation tests, which may be unreliable in patients treated with Hemlibra®,by estimating the proportion of targeted prescribers with correct responses to risk knowledge questions.
- Assess self-reported prescriber adherence to the additional RMMs, by estimating the proportion of targeted prescribers whose responses to the practice-related questions are consistent with the Guide for Healthcare Professionals.

Patient/carer survey

- Assess patient/carer awareness of the Hemlibra® educational program by estimating the proportion of patients who acknowledge having received and read the Patient/Carer Guide and Patient Alert Card.
- Assess patient/carer knowledge of:
 - the important identified risks of TMA and TEs that may occur if a cumulative amount of >100U/kg/24 hours for 24 hours or more of aPCC is used concomitantly with Hemlibra® and
 - the important potential risk of life-threatening bleeding due to misinterpretation of the standard coagulation tests, which may be unreliable in patients treated with Hemlibra®,by estimating the proportion of patients/carers with correct responses to risk knowledge questions.
- Assess patient/carer self-reported adherence to the additional RMMs, which will be evaluated by estimating the proportion of patients/carers whose responses to the questions are consistent with the Patient/Carer Guide and Patient Alert Card.

The objectives for the survey will be aligned with any key elements to be addressed in these studies provided by the Pharmacovigilance Risk Assessment Committee (PRAC).

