- Bypassing dosing guidance in their patients receiving Hemlibra® prophylaxis (tick boxes with answers that are either consistent or inconsistent with the additional RMMs)

Patient/carer survey

- Variables related to the patients treated with Hemlibra®:
 - Completion by patient or carer
 - Patient age (years)
 - Time since last dose of Hemlibra® (tick boxes with ranges of treatment duration in months)
 - Diagnosis with FVIII inhibitors (yes/no)
 - Severity of disease (mild/moderate/severe)
 - Receiving at least 4 doses of Hemlibra® in the last 6 months (yes/no)
- Variables related to the patients' awareness of the Hemlibra® educational program, or the awareness of their carer if the patient is under the age of 18:
 - Receipt of Patient Alert Card and Patient/Carer Guide (tick boxes for receipt)
 - Discussion with HCPs of risks associated with the use of Hemlibra® (yes/no)
 - Reading of the received educational materials (yes/no)
- Variables related to the patients' knowledge about the risks of Hemlibra®, or the knowledge of their carer if the patient is under the age of 18:
 - Knowledge of risks associated with the use of Hemlibra® (tick boxes with answers that are either consistent or inconsistent with the additional RMMs)
 - Knowledge that the Patient Alert Card should be carried at all times (tick boxes with answers that are either consistent or inconsistent with the additional RMMs)
 - Knowledge that Hemlibra® use can affect laboratory tests on blood clotting (true/false)
 - Knowledge of aPCC dosing and risks of concomitant use with Hemlibra® therapy (true/false statements)
- Variables related to the patients' self-reported adherence to the educational measures by correct implementation of the additional RMMs, or the self-reported adherence of their carer if the patient is under the age of 18:
 - Showing the Patient Alert Card to health care professionals (yes/no)
 - For patients taking aPCC while taking Hemlibra®:
 - Taking a first dose of aPCC of <50U/kg
 - Contacting their HCP before increasing the dose of aPCC above 50U/kg (yes/no/not applicable)
 - Not taking >100U/kg/24 hours for 24 hours or more (yes/no)

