8.7.4 Questionnaire Analysis

Analysable questionnaires are those completed and submitted by the participants on the web. If the questionnaire is just filled on the web but not submitted, the questionnaire will not be analysed and will be discarded.

Analysis will be done on questions common to all HCPs and patients/carers as well as on a limited number of questions presented to the subgroup of patients with concomitant use of aPCC and Hemlibra® (or their carers).

For each question, the number and percentage of participants correctly answering each question will be presented. Individual awareness, knowledge, and adherence values will be calculated as the percentage of correctly answered questions; values will range from 0 to 100% with 100% representing the percentage of all questions in the category being answered correctly.

Awareness questions

- HCP questionnaire: Q8 and Q9
- Patient/carer questionnaire: Q1 and Q2

Knowledge questions

- HCP questionnaire: Q10, Q11, and Q12
- Patient/carer questionnaire
 - All: Q3, Q4, Q5, and Q6

Adherence questions

- HCP questionnaire: Q13, Q14, Q15, Q16, and Q17
- Patient/carer questionnaire
 - All: Q11
 - Additional questions for patients (or their carers) taking aPCC and Hemlibra: Q8, Q9, and Q10

In a first step, calculations will be performed on raw data. No projection factor will be applied to generalize the results to the entire prescribers' universe. As a consequence, the line "Overall - unweighted results" will show only the results observed on the overall sample and will not reflect the geographies' universe since this sample is not proportional to the size of the lists in each geography.

If possible, in a second step, the results will be weighted according to the real proportion of HCPs or patients/carers in a geographical region in order to accurately reflect the population that the survey seeks to measure.

Possible *participation* bias will be assessed by comparing the distributions of available characteristics (e.g., geography, type of setting [e.g., haemophilia treatment centre or HCCC], and speciality, if applicable and feasible) between respondents and non-respondents.

Assessment of success

The proportions of correct and appropriate answers to selected questions asked in the questionnaire will be presented for HCPs or patients/carers who provided answers to those questions, as outlined below.

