Successful outcomes for the effectiveness of risk minimisation measures in the aspects of awareness, knowledge, and adherence are defined a priori by the following target levels:

For HCPs

- Awareness: Proportion of HCPs aware of the Hemlibra® educational program (Q8 and Q9) – Success: $\geq 75\%$
- Knowledge: Proportion of HCPs with knowledge of the important identified risks and potential risks associated with Hemlibra treatment (Q10, Q11, and Q12) – Success $\geq 60\%$
- Adherence: Proportion of HCPs self-reporting adherence to the additional RMMs for Hemlibra (Q13, Q14, Q15, Q16, and Q17) – Success $\geq 75\%$

For patients/carers

- Awareness: Proportion of patients/carers aware of the of the Hemlibra® educational program (Q1 and Q2) – Success: $\geq 60\%$
- Knowledge: Proportion of patients/carers with knowledge of the important identified risks and potential risks associated with Hemlibra treatment (Q3, Q4, Q5, and Q6) – Success: $\geq 60\%$
- Adherence: Proportion of patients/carers self-reporting adherence to the additional RMMs for Hemlibra (Q11) – Success: $\geq 60\%$

- Proportion of patients taking aPCC and Hemlibra (or their carers) self-reporting adherence to the additional RMMs specific for use of aPCC and Hemlibra (Q8, Q9, and Q10) - Success: $\geq 60\%$

Overall success is defined as success on all three domains measures (awareness, knowledge and adherence) for both HCPs and patients/carers.

Exploratory analysis of HCPs with higher success rates will also be performed and the percentage of HCPs who answered 80% and 90% of the questions correctly in each of domain will be calculated.

A sensitivity analysis will be performed to assess and compare the results of HCPs who were investigators in Hemlibra clinical studies (i.e., HAVEN) with the ones from HCPs who have prescribed Hemlibra exclusively in routine clinical practice.

Profile of HCPs with incorrect answers

The profile of HCPs with incorrect answers to the questions related to the three success factors will be described using all available and relevant HCPs characteristics collected in the survey (e.g., geography, speciality, duration of practice, practice setting) and past experience with Hemlibra® (number of patients prescribed).

Profile of patients with incorrect answers

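### The awareness rules do not estimate the share of all respondents who received and read the materials, so the awareness target can be met when that share falls short of it

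*Protocol*

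**What the plan says.** **Objective.** Protocol section 7.2 assesses HCP awareness by "estimating the proportion of targeted prescribers who acknowledge having received and read the relevant educational materials". For patients and carers it is "estimating the proportion of patients who acknowledge having received and read the Patient/Carer Guide and Patient Alert Card". Both describe one joint condition per person, over everyone targeted.

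**Denominator.** Section 8.7.1 expresses the proportions of correct answers among those who answered, and adds: "If missing data exists, it will not be counted as a denominator in proportions". Under Assessment of success, section 8.7.4 says the proportions "will be presented for HCPs or patients/carers who provided answers to those questions, as outlined below".

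**Score.** Section 8.7.4 gives each respondent an awareness value equal to the percentage of the category's questions answered correctly. The synopsis (Data Analysis) defines success on overall scores: at least 75% for HCP awareness and at least 60% for patients and carers.

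**Criterion.** Section 8.7.4 names the HCP measure as "Proportion of HCPs aware of the Hemlibra® educational program (Q8 and Q9"), and uses questions Q1 and Q2 for patients and carers. It does not say how two questions make one person aware.

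**Routing.** Sections 8.4.2 and 8.7.5 force an answer before the respondent can move on. Section 8.6.1 states "Skip patterns are clearly indicated" but does not say for which questions. Section 8.3 lists the patient reading variable as "Reading of the received educational materials (yes/no"). The HCP reading variable there is not tied to receipt.

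**The concern.** Because answers are forced and only submitted questionnaires are analysed, few answers can be missing through omission. The main remaining source of an unanswered question is a skip pattern. A skip triggered by not having received the materials is not random, although section 8.7.5 expects missing data to be few and random. Under an answered-only denominator, such a person leaves the reading proportion instead of counting as a failure.

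The percentage-correct score raises a second problem that needs no skip. A respondent who received the material but did not read it meets half of the awareness items, yet does not meet the objective at all.

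Both effects push the result upwards. People whom distribution did not reach, or who did not read what they received, are the failures this survey is meant to find. Awareness is also one of the three domains that must all succeed for overall success.

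**Working it through.** **Inputs.** From the Protocol: targets of 75% (HCPs) and 60% (patients/carers), and planned sizes of 40 and 70. The Protocol gives no expected awareness figure, so there is none to reproduce. Assumed: receipt rate r from 0.50 to 0.95, and reading rate among receivers q from 0.80 to 0.95. Also assumed: one awareness question covers receipt and the other reading. Partial receipt of several tools is not modelled.

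**Quantity in the objective:** received and read = r×q.

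**Effect 1: answered-only denominator, if non-receivers skip the reading question.**

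- Reading percentage = rq/r = q.
- Overstatement = q − rq = q(1−r).
- Smallest over the assumed range: 0.80×0.05 = 4 points. Largest: 0.95×0.50 = 47.5 points.
- HCPs, 40 respondents, 32 received, 29 read: 29/32 = 90.6% against 29/40 = 72.5%. The target is 75%.
- Patients, 70 respondents, 49 received, 41 read: 41/49 = 83.7% against 41/70 = 58.6%. The target is 60%.
- At q = 0.90 the reading percentage meets the target while received-and-read does not whenever r is below 0.75/0.90 = 83% (HCPs) or 0.60/0.90 = 67% (patients).
- If everyone is asked the reading question, non-receivers answer no, and this effect is zero.

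**Effect 2: percentage-correct score, whatever the routing.**

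- A respondent who received and read scores 100, one who received only scores 50, and one who did neither scores 0. A skipped non-receiver has 0 of 1 correct instead of 0 of 2, which is still 0.
- Mean score = rq + 0.5×r(1−q) = r(1+q)/2.
- Excess over the objective = r(1+q)/2 − rq = r(1−q)/2.
- Over the assumed range this runs from 0.50×0.05/2 = 1.25 points to 0.95×0.20/2 = 9.5 points.

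| Illustration | Mean score | Received and read | Target |
|---|---|---|---|
| Patients: 50% both, 20% received only, 30% neither | 50 + 10 = 60% | 50% | 60% |
| Patients: 41 both, 8 received only, 21 neither | (4100 + 400)/70 = 64.3% | 58.6% | 60% |
| HCPs: 29 both, 3 received only, 8 neither | (2900 + 150)/40 = 76.3% | 72.5% | 75% |
| HCPs: 65% both, 10% received only, 25% neither | 65 + 5 = 70% | 65% | 75% |

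The first three rows meet the target on the score and miss it on the objective. In the fourth, both miss.

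The score meets the target while the objective misses it when 2T/(1+q) ≤ r < T/q, where T is the target. At q = 0.90 that is r from 1.5/1.9 = 78.9% to 83.3% for HCPs, and from 1.2/1.9 = 63.2% to 66.7% for patients.

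**The case against.** The strongest reply is that the routing cannot be seen. The questionnaires in Appendices 2 to 4 are not shown, and the skip patterns may concern only the questions for patients who also use aPCC. This stands. A reader might infer that the denominator rule does remove non-receivers and that awareness is therefore overstated. The documents do not support that as fact. The patient variable suggests it by its wording, but the HCP variable does not. Section 8.3 also lists three patient awareness variables (receipt, discussion with HCPs, reading) against two awareness questions, so which variables Q1 and Q2 carry is not established.

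A reader might also put the 60% mean score in the first illustration down to the denominator rule. It is not: non-receivers are in that mean and score zero. The excess is the half credit for receipt alone.

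The criterion in 8.7.4 can also be read as a single person-level proportion over both questions, and no criterion rests on the reading percentage alone. That reading would agree with the objective. However, the protocol does not state it, and the synopsis sets success on overall scores. The per-question results would still show low receipt, so non-receivers would not be hidden, but the success decision could still go the other way.

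Finally, details of derived scores may be left to the statistical analysis plan. Here the protocol does fix an answered-only denominator and a percentage-correct score, and neither matches its own objective. The mismatch lies in stated rules, not in absent detail.

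**Conclusion.** The point holds as a mismatch between the awareness objective and the rules meant to estimate it. It does not hold as proof that awareness will be overstated.

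The denominator part is conditional. If non-receivers skip the reading question, its percentage is too high by q(1−r), which is 4 to 47.5 points over the assumed range. If they do not skip it, there is no such effect. The case is better supported for patients than for HCPs.

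The scoring part does not depend on routing, but it assumes that the two awareness questions are receipt and reading. The mean score then exceeds the received-and-read share by r(1−q)/2, or 1.25 to 9.5 points over the same range. That can carry a result across the 60% or 75% target, though only in a narrow band of receipt rates. All receipt and reading rates are illustrative.

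**What to change.** In sections 8.7.1 and 8.7.4, and in the statistical analysis plan, state for the awareness success criterion that:

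- the denominator is all analysable (submitted) questionnaires;
- a respondent is aware only if they report both receiving and reading the relevant materials;
- anyone not asked the reading question because of non-receipt counts as not aware.

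Report reading among receivers as a descriptive figure only, and align the synopsis wording on overall scores for this domain.

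This needs a short insertion and no new data, and it gives the section 7.2 quantity whichever routing the questionnaires use. The cost is that the awareness figure will be equal to or lower than under the present rules, so the targets may be harder to meet.
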